7.4.3. Overall Survival

Overall survival is defined as the interval between the randomization date and the date of death due to any cause. Date of death will be determined using the Death Report, the Survival Follow-Up, and the Participant Status eCRFs. Participants who are lost-to-follow-up or still alive at the time of analysis will be right-censored at the earlier of the date the participant was last known alive and the clinical data cutoff date for the analysis. The last known alive date is defined as the later of the last study visit and the date the participant was last known alive from the Survival Follow-Up and Participant Status eCRFs. Partial death dates will be handled using the rules described in Section 4.1.5.

The treatment difference in survival for parsaclisib plus ruxolitinib and placebo plus ruxolitinib will be assessed by a log-rank test on the ITT population and PP population stratified for baseline (or screening, if applicable) platelet count and DIPSS category. The strata identified in the randomization process will be used for the analysis. In the event that stratification level combinations have limited numbers of participants, 2 or more of the strata may be combined to better facilitate estimation of the overall HR.

[figure not shown]
The HR estimate and CIs will be estimated based on a stratified Cox proportional hazards model using the same stratification factors as for the log-rank test with Efron's method (1977) accounting for ties in death days.

[figure not shown]
Kaplan-Meier time-to-event curves will be presented by treatment group. Median survival will be estimated using the KM method. Confidence intervals for median survival time will be calculated using the generalization of Brookmeyer and Crowley's method (1982) with log-log transformation (Klein and Moeschberger 1997).

[figure not shown]
The ITT population will be used for the analysis of OS.

[figure not shown]
A sensitivity analysis of OS using PP population will be provided. The sensitivity analysis of OS will be analyzed using the rank-preserving structural failure time method to adjust the bias in OS due to crossover.

[figure not shown]
Due to the early study termination, the number of deaths observed was limited; therefore, the OS analyses will not be performed. A listing of deaths will be provided instead.

[figure not shown]

[figure not shown]

9. SAFETY AND TOLERABILITY

[Appendix A](#) provides a list of data displays. Sample data displays are included in a separate document.

9.1. General Considerations

The safety analyses, including frequency and severity of AEs and SAEs and mean change and percentage change in vital signs, ECGs, and lab parameters, will be summarized by treatment group in the safety population.

Summary tables may be replaced with listings when appropriate. For instance, an AE frequency table may be replaced with a listing if it only contains a few unique PTs reported on relatively few participants.

Safety analyses for treatment comparisons will exclude data collected after treatment crossover. Data post-treatment crossover will be analyzed separately and descriptively without any treatment comparisons. Day 1 of crossover will be used for the crossover participants in the crossover phase.

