3. STUDY DESIGN

This is a Phase 3, randomized, double-blind study of the combination of the PI3K δ inhibitor parsaclisib or matching placebo and the JAK1/2 inhibitor ruxolitinib in participants with PMF or secondary MF (PPV-MF or PET-MF) who have had suboptimal response while receiving ruxolitinib monotherapy. Participants must meet Protocol-defined criteria for suboptimal response to ruxolitinib monotherapy. After participants have been determined to meet all criteria, they will be randomized to 1 of 2 treatment groups and will receive parsaclisib or matching placebo at a dose of 5 mg QD beginning on Day 1. Participants will also continue to receive the stable dose of ruxolitinib they were taking for the 8 weeks prior to Day 1. Both parsaclisib/matching placebo and ruxolitinib dosing will continue for the duration of participation in the study. [Figure 1](#) presents the study design schema.

Figure 1: Study Design Schema

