4.1.2. Day 1 of Crossover for Crossover Participants

For participants who cross over from placebo plus ruxolitinib to parsaclisib plus ruxolitinib, Day 1 of crossover is the date the first dose of open-label parsaclisib is administered to the participants.

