5.2. Treatment Groups

This is a randomized, double-blind, parallel treatment group design. Participants will be summarized by treatment group. A participant randomized to the control group may make a crossover to the active treatment prior to Week 24 if the participant meets the criteria for an early crossover. Unless specified, efficacy and safety analyses for between-treatment comparisons (parsaclisib + ruxolitinib vs placebo + ruxolitinib) will be conducted using the data truncated at the time of treatment crossover for those participants who made an early treatment crossover prior to Week 24. Data collected after the treatment crossover will be summarized and tabulated separately without treatment comparisons.

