9.2. Adverse Events

9.2.1. Adverse Event Definitions

A TEAE is any AE either reported for the first time or worsening of a pre-existing event after the first dose of study drug until 30 to 35 days after the last dose of study drug. Analysis of AEs (as discussed below) will be limited to TEAEs, but data listings will include all AEs regardless of their timing in relation to study drug administration. For purposes of analysis, all AEs will be considered TEAEs unless the AE can unequivocally be defined as not treatment-emergent.

Adverse events will be tabulated by MedDRA PT and SOC. Severity of AEs will be graded using the NCI CTCAE v5. The CTCAE reporting guidelines and grading details are available on the Cancer Therapy Evaluation Program website.

The subset of AEs considered by the investigator to be related to study drug will be considered to be treatment-related AEs. If the investigator does not specify the relationship of the AE to study

drug, the AE will be considered to be treatment-related. The incidence of AEs and treatment-related AEs will be tabulated. In addition, serious TEAEs will also be tabulated.

To summarize TEAEs using the life-table method, the time to first occurrence of a TEAE is defined as the interval between the date of first dose of study drug and the date of the first occurrence of a TEAE. Participants who have not experienced a TEAE at the time of analysis will be right-censored at the earlier of 30 to 35 days after the last dose of study drug and the date of last study visit through the end of safety follow-up. The effective sample size is defined as the number of participants at the beginning of interval minus half the participants censored in the interval. The conditional proportion is calculated as the number of first events divided by the effective sample size in the interval. If participants have missing or partial last dose dates of study drug, the partial or missing dates will be handled using the rules explained in Section 4.1.5. Any missing onset date of a TEAE will be handled according the following rules:

- If completely missing, then Day 1 will be used.
- If only the day is missing, then the first day of the month or Day 1, whichever is later, will be used.
- If both the month and day are missing, then 01 JAN of the year or Day 1, whichever is later, will be used.

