9.2.3. Adverse Event Summaries

An overall summary of AEs by treatment group will include the following:

- Number (%) of participants who had any TEAEs
- Number (%) of participants who had any serious TEAEs
- Number (%) of participants who had any Grade 3 or higher TEAEs
- Number (%) of participants who had any TEAEs related to parsaclisib
- Number (%) of participants who had any TEAEs related to ruxolitinib
- Number (%) of participants who had any TEAEs related to parsaclisib or ruxolitinib
- Number (%) of participants who temporarily interrupted parsaclisib because of TEAEs
- Number (%) of participants who temporarily interrupted ruxolitinib because of TEAEs
- Number (%) of participants who permanently discontinued parsaclisib because of TEAEs
- Number (%) of participants who permanently discontinued ruxolitinib because of TEAEs
- Number (%) of participants who had parsaclisib dose reductions because of TEAEs
- Number (%) of participants who had ruxolitinib dose reductions because of TEAEs
- Number (%) of participants who had any fatal TEAEs

The following summaries will be produced by MedDRA term (if 10 or fewer participants appear in a table, a listing may be appropriate):

- Summary of TEAEs by MedDRA SOC and PT
- Summary of TEAEs by MedDRA PT in decreasing order of frequency
- Summary of TEAEs by MedDRA SOC, PT, and CTCAE grade category
- Summary of Grade 3 or higher TEAEs by MedDRA SOC and PT
- Summary of Grade 3 or higher TEAEs by MedDRA PT in decreasing order of frequency
- Summary of serious TEAEs by MedDRA SOC and PT
- Summary of serious TEAEs by MedDRA PT in decreasing order of frequency
- Summary of parsaclisib/placebo treatment-related TEAEs by MedDRA SOC and PT
- Summary of ruxolitinib treatment-related TEAEs by MedDRA SOC and PT
- Summary of parsaclisib/placebo/ruxolitinib treatment-related TEAEs by MedDRA SOC and PT
- Summary of parsaclisib/placebo treatment-related TEAEs by MedDRA PT in decreasing order of frequency
- Summary of ruxolitinib treatment-related TEAEs by MedDRA PT in decreasing order of frequency
- Summary of parsaclisib/placebo treatment-related TEAEs by MedDRA SOC, PT, and CTCAE grade category
- Summary of ruxolitinib treatment-related TEAEs by MedDRA SOC, PT, and CTCAE grade category
- Summary of Grade 3 or higher parsaclisib/placebo treatment-related TEAEs by MedDRA SOC and PT
- Summary of Grade 3 or higher ruxolitinib treatment-related TEAEs by MedDRA SOC and PT

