- Summary of parsaclisib/placebo treatment-related serious TEAEs by MedDRA SOC and PT
- Summary of ruxolitinib treatment-related serious TEAEs by MedDRA SOC and PT
- Summary of TEAEs with a fatal outcome by MedDRA SOC and PT
- Summary of TEAEs leading to parsaclisib/placebo dose reduction by MedDRA SOC and PT
- Summary of TEAEs leading to ruxolitinib dose reduction by MedDRA SOC and PT
- Summary of TEAEs leading to parsaclisib/placebo dose interruption by MedDRA SOC and PT

- Summary of TEAEs leading to ruxolitinib dose interruption by MedDRA SOC and PT
- Summary of TEAEs leading to discontinuation of parsaclisib/placebo by MedDRA SOC and PT
- Summary of TEAEs leading to discontinuation of ruxolitinib by MedDRA SOC and PT
- Summary of TEAEs by MedDRA PT: life-table method
- Summary of TEAEs by MedDRA SOC and PT: life-table method
- Summary of treatment-emergent AESIs by MedDRA PT
- Median time to the first onset of treatment-emergent AESIs by MedDRA PT
- Median longest duration of treatment-emergent AESIs by MedDRA PT

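### Grade 3+, serious, fatal and discontinuation TEAEs are compared as crude percentages although crossover shortens observation on placebo only, and no time-adjusted display is planned for them

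*SAP*

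**What the plan says.** Crossover is one-way. Section 5.2: "A participant randomized to the control group may make a crossover to the active treatment prior to Week 24", subject to criteria. Section 4.1.2 defines a crossover Day 1 only for participants moving from placebo to open-label parsaclisib.

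For safety, Section 9.1 says: "Safety analyses for treatment comparisons will exclude data collected after treatment crossover". It adds: "Data post-treatment crossover will be analyzed separately and descriptively without any treatment comparisons".

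Nothing equivalent shortens the parsaclisib arm. Section 3: "Both parsaclisib/matching placebo and ruxolitinib dosing will continue for the duration of participation in the study". Under Section 9.2.1 a TEAE counts "until 30 to 35 days after the last dose of study drug". No AE table is limited to a common period such as Day 1 to Week 24.

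Section 9.2.3 sets the measures. The overall summary is made of lines such as "Number (%) of participants who had any Grade 3 or higher TEAEs", with matching lines for serious, fatal, related, interruption, reduction and discontinuation TEAEs. Appendix A lists the corresponding tables (3.2.1, 3.2.6 to 3.2.9, 3.2.16, 3.2.20.1 and 3.2.20.2) without an exposure-adjusted version.

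Two kinds of display do use follow-up time. One is the life-table pair, "Summary of TEAEs by MedDRA PT: life-table method" and its SOC/PT counterpart (Tables 3.2.22 and 3.2.23). The other is Kaplan-Meier time to first onset for each AESI (Section 9.2.2, Table 3.2.24.2, Figure 4.3.1).

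**The concern.** A crude percentage counts participants with at least one event over whatever time they were observed. If one arm is watched for less time, its percentage falls even when the underlying risk is the same. Here the shortening comes from a rule that can apply only to placebo, and it affects the tables on which a judgement about added harm mainly rests.

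Table 1 makes the comparison of safety and tolerability a secondary objective, to be assessed by AE frequency and severity. For Grade 3+, serious, fatal and discontinuation events, the planned tables do not let a reader separate a true excess on parsaclisib from longer observation, or see how far the two offset each other.

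**Working it through.** The SAP gives no safety figure to reproduce, so this is an illustration with the same constant event rate in both arms.

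**Inputs**
- Crossover at Week 24: tc = 24 × 7 / 365.25 = 0.46 year. *Assumption*; the SAP does not state the timing.
- Share of placebo participants crossing over, q: *assumption*, 25% to 100%.
- Event rate h, equal in both arms: *assumption*, 0.187 to 1.0 per patient-year. The lower end is ln 2 / 3.7, from the control median survival in Section 3.3.
- Follow-up without crossover, T: *assumption*, 1.0 to 3.5 years. Section 3.3 expects a 4-year study, but it ended early and actual follow-up is not stated.

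**Formulas**
- Parsaclisib: 1 − exp(−hT)
- Placebo: q[1 − exp(−h·tc)] + (1 − q)[1 − exp(−hT)]

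**Worked case**, h = 0.3, T = 1:
- Full follow-up: 1 − exp(−0.3) = 25.9%.
- Cut at Week 24: 1 − exp(−0.3 × 0.46) = 12.9%.
- Placebo with 25% crossing: 0.25 × 12.9 + 0.75 × 25.9 = 22.7%. With 50%: 19.4%. With 100%: 12.9%.

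| Rate per patient-year | Follow-up | Parsaclisib | Placebo, 25% cross | Placebo, 50% cross | Placebo, 100% cross |
|---|---|---|---|---|---|
| 0.3 | 1 year | 25.9% | 22.7% | 19.4% | 12.9% |
| 0.3 | 1.5 years | 36.2% | 30.4% | 24.6% | 12.9% |
| 0.6 | 1 year | 45.1% | 39.9% | 34.6% | 24.1% |
| 0.6 | 1.5 years | 59.3% | 50.5% | 41.7% | 24.1% |

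Over the whole assumed range the crude ratio runs from 1.12 (h = 1.0, T = 1, q = 25%) to 5.83 (h = 0.187, T = 3.5, q = 100%).

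**After adjustment.** Divide first events by time at risk up to the first event, crossover or end of follow-up. For h = 0.3, T = 1, q = 50%, parsaclisib gives 0.259 events over 0.259 / 0.3 = 0.864 year per participant, and placebo 0.194 over 0.194 / 0.3 = 0.647 year. Both rates are 0.30 per patient-year.

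**When the direction fails.** Let d be the treatment discontinuation rate, ignoring the 30 to 35 days after last dose. The crude percentage to time t is then h/(h + d) × [1 − exp(−(h + d)t)]. Take h = 0.6, T = 1.5, q = 50% and d = 0.3 on placebo:
- Placebo: 36.0%.
- Parsaclisib with the same d = 0.3: (0.6 / 0.9) × [1 − exp(−1.35)] = 49.4%.
- Parsaclisib with d = 0.5: 44.1%; d = 1.0: 34.1%; d = 2.0: 22.6%.

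In this example the sign has reversed by d = 1.0 per year.

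**Do the existing time-based displays handle crossover?** The life-table rule in Section 9.2.1 censors event-free participants at the earlier of 30 to 35 days after last dose of study drug and the last study visit; it does not mention crossover. Section 9.2.2 censors participants without an AESI at the time of analysis. If later AESIs of a crossed-over placebo participant are excluded under Section 9.1 but the participant stays at risk until the analysis, placebo risk is understated.

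**The case against.** **The exclusion rule is sound.** Keeping post-crossover data in the placebo arm would charge parsaclisib events to placebo. This stands: the weakness is the pairing of the cut with crude percentages, not the cut.

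**The direction is not certain.** A reader might infer that the tables are simply biased against parsaclisib. The SAP does not support that. Parsaclisib observation also ends, shortly after last dose, and faster discontinuation there can cancel or reverse the gap. This stands, but it means the percentages may mislead in either direction, which is still a reason to show time at risk.

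**The doubling is an extreme.** A reader might take 25.9% against 12.9% as the expected distortion. It requires every placebo participant to cross over at Week 24. The SAP describes only criteria-based crossover before Week 24 in any detail and gives no share. Early termination also makes long follow-up less likely. This stands; with 25% crossing, the same inputs give a gap of 3.3 percentage points.

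**Time-aware displays already exist.** It would be wrong to say that there are none. All TEAEs have life-table displays, and AESIs, which include serious conditions such as intestinal perforation and pneumonitis, have Kaplan-Meier onset. Exposure duration by arm (Tables 3.1.1 and 3.1.2) and a listing of crossover participants (2.3.2) would also reveal unequal observation. None of these adjusts the Grade 3+, serious, fatal or discontinuation percentages.

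**Little depends on it formally.** No safety test is planned, so no error rate is affected, and Section 9.1 allows sparse tables, as fatal events may be, to become listings. This stands and limits the weight of the point.

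**Conclusion.** The point holds in a limited form. For Grade 3+, serious, fatal and discontinuation TEAEs, the SAP compares crude percentages over observation periods that its own crossover rule makes unequal, and lists no time-adjusted display for those categories.

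Given otherwise similar follow-up, equal risks would look higher on parsaclisib. At 0.3 events per patient-year, 1 year of follow-up and crossover at Week 24, the crude ratio is 1.14, 1.34 or 2.01 for 25%, 50% or 100% crossing over. These are illustrations, not estimates: the gap is small if few crossed over, and its sign depends on discontinuation in each arm. The effect is on the reading of a descriptive comparison. A low-cost correction is worthwhile because that comparison is a stated objective.

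**What to change.** For the overall summary and the Grade 3+, serious, fatal and discontinuation tables, do one of the following and keep the crude percentages beside it:
- add participants with a first event per 100 patient-years, with time at risk ending at the first event, crossover or the end of the TEAE window, whichever comes first; or
- add a Day 1 to Week 24 comparison, also cut at crossover.

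For the life-table tables and the AESI Kaplan-Meier analyses, state in Sections 9.2.1 and 9.2.2 that placebo participants are censored at crossover. AESIs then need no further rate table. In the same edit, align Section 5.2, which ties truncation to crossover before Week 24, with Section 9.1, which excludes data after any crossover.

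The cost is a few columns from data already collected. Rates assume roughly constant risk. A Week 24 cut omits later events and, if shown as a crude percentage, still leaves early crossovers with less time. Because early crossover depends on meeting criteria, censoring there may be informative, and neither option removes that; a footnote should say so.

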9.2. Adverse Events

9.2.1. Adverse Event Definitions

A TEAE is any AE either reported for the first time or worsening of a pre-existing event after the first dose of study drug until 30 to 35 days after the last dose of study drug. Analysis of AEs (as discussed below) will be limited to TEAEs, but data listings will include all AEs regardless of their timing in relation to study drug administration. For purposes of analysis, all AEs will be considered TEAEs unless the AE can unequivocally be defined as not treatment-emergent.

Adverse events will be tabulated by MedDRA PT and SOC. Severity of AEs will be graded using the NCI CTCAE v5. The CTCAE reporting guidelines and grading details are available on the Cancer Therapy Evaluation Program website.

The subset of AEs considered by the investigator to be related to study drug will be considered to be treatment-related AEs. If the investigator does not specify the relationship of the AE to study

drug, the AE will be considered to be treatment-related. The incidence of AEs and treatment-related AEs will be tabulated. In addition, serious TEAEs will also be tabulated.

To summarize TEAEs using the life-table method, the time to first occurrence of a TEAE is defined as the interval between the date of first dose of study drug and the date of the first occurrence of a TEAE. Participants who have not experienced a TEAE at the time of analysis will be right-censored at the earlier of 30 to 35 days after the last dose of study drug and the date of last study visit through the end of safety follow-up. The effective sample size is defined as the number of participants at the beginning of interval minus half the participants censored in the interval. The conditional proportion is calculated as the number of first events divided by the effective sample size in the interval. If participants have missing or partial last dose dates of study drug, the partial or missing dates will be handled using the rules explained in Section 4.1.5. Any missing onset date of a TEAE will be handled according the following rules:

- If completely missing, then Day 1 will be used.
- If only the day is missing, then the first day of the month or Day 1, whichever is later, will be used.
- If both the month and day are missing, then 01 JAN of the year or Day 1, whichever is later, will be used.

9.2.2. Adverse Events of Special Interest

The following TEAEs, regardless of seriousness, will be tabulated by MedDRA PT for the safety population for each treatment group.

- Colitis
- Diarrhea of Grade 2 or higher
- Rash of Grade 2 or higher
- Pneumonitis
- Dermatitis exfoliative
- Intestinal perforation
- Cytomegalovirus infection
- Herpes simplex infection, including oral herpes and genital herpes as AE terms
- Herpes (varicella) zoster virus infection, including herpes zoster, shingles, and VZV as AE terms
- Pneumocystis jirovecii infection
- ALT increased $\geq 5 \times$ ULN
- AST increased $\geq 5 \times$ ULN

Adverse events of special interest should be captured in the eCRF.

The time to onset of the first occurrence of each AESI will be analyzed using the KM method. Median time to onset of the first occurrence of each AESI will be estimated by the KM method. Participants with no AESI at the time of analysis will be censored at the time of analysis.

The longest duration of AESI will be analyzed using the KM method for participants in the safety population with at least 1 occurrence of the AESI. The median longest duration of each AESI will be estimated by the KM method. Participants whose AESI was not resolved at the time of analysis will be censored at the time of the analysis. Participants with nonserious TEAEs not resolved by 35 days after the end-of-treatment visit will be censored at 35 days after the end-of-treatment visit.

Two consecutive AESIs with different toxicity grades but with the start date of the later AESI overlapped with the end date of the previous AESI are considered as 1 AESI in calculating the duration of AESI.

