7.4.2.3. Mean Change and Percentage Change in Myelofibrosis Symptom Assessment Form v4.0 Total Symptom Score

The mean change and percentage change from baseline to Week X will be calculated using the following formula:

$$\% \text{ change} = 100 \times (\text{Week X total score} - \text{baseline total score}) / \text{baseline total score}.$$

The mean change and percentage change in TSS, the 7 individual scores, and the total score of the 3 spleen-related symptoms (including abdominal discomfort, pain under left ribs, and early satiety) from baseline to Week X will be summarized descriptively by treatment group and every 4 weeks using the ITT population. Missing values will not be imputed.

A plot of percentage change from baseline in MFSAF TSS at each visit will be provided.

7.4.2.4. Time to the First $\geq 50\%$ Reduction in Myelofibrosis Symptom Assessment Form v4.0 Total Symptom Score

The time to the first $\geq 50\%$ reduction in TSS is defined as the time from randomization to the first time participants have a $\geq 50\%$ reduction in TSS. The daily TSS will be calculated according to the algorithm defined in Section 7.4.2.1.2. Participants with valid, calculated baseline TSS and at least 1 postbaseline TSS who do not have $\geq 50\%$ reduction in TSS at the time of analysis will be censored at the time of the last valid calculated TSS. If the participants have no valid, calculated baseline or postbaseline TSS, they will be censored at the date of randomization.

The stratified log-rank test will be used to compare time to the first $\geq 50\%$ reduction in TSS between the 2 treatment groups in the ITT population at a 1-sided 2.5% significance level, stratified for baseline (or screening, if applicable) platelet count and DIPSS category. The strata identified in the randomization process will be used for the analysis.

Kaplan-Meier curves for the time to the first $\geq 50\%$ reduction in TSS will be presented by treatment group. The KM estimate of median time to the first $\geq 50\%$ reduction in TSS will be presented with its 95% CI. The 95% CI will be calculated using the generalization of method of Brookmeyer and Crowley (1982) with log-log transformation (Klein and Moeschberger 1997).

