3.2.15.1	Summary of Parsaclisib/Placebo Treatment-Related Serious Treatment-Emergent Adverse Events by MedDRA System Organ Class and Preferred Term	Safety	X
3.2.15.2	Summary of Ruxolitinib Treatment-Related Serious Treatment-Emergent Adverse Events by MedDRA System Organ Class and Preferred Term	Safety	X
3.2.16	Summary of Treatment-Emergent Adverse Events With a Fatal Outcome by MedDRA System Organ Class and Preferred Term	Safety	X
3.2.18.1	Summary of Treatment-Emergent Adverse Events Leading to Parsaclisib/Placebo Dose Reduction by MedDRA System Organ Class and Preferred Term	Safety	X
3.2.18.2	Summary of Treatment-Emergent Adverse Events Leading to Ruxolitinib Dose Reduction by MedDRA System Organ Class and Preferred Term	Safety	X
3.2.19.1	Summary of Treatment-Emergent Adverse Events Leading to Parsaclisib/Placebo Dose Interruption by MedDRA System Organ Class and Preferred Term	Safety	X
3.2.19.2	Summary of Treatment-Emergent Adverse Events Leading to Ruxolitinib Dose Interruption by MedDRA System Organ Class and Preferred Term	Safety	X
3.2.20.1	Summary of Treatment-Emergent Adverse Events Leading to Discontinuation of Parsaclisib/Placebo by MedDRA System Organ Class and Preferred Term	Safety	X
3.2.20.2	Summary of Treatment-Emergent Adverse Events Leading to Discontinuation of Ruxolitinib by MedDRA System Organ Class and Preferred Term	Safety	X
3.2.22	Summary of Treatment-Emergent Adverse Events by MedDRA Preferred Term: Life-Table Method	Safety	X

Table No.	Title	Population	Standard
3.2.23	Summary of Treatment-Emergent Adverse Events by MedDRA System Organ Class and Preferred Term: Life-Table Method	Safety	X
3.2.24.1	Summary of Treatment-Emergent Adverse Events of Special Interest by MedDRA Preferred Term	Safety	X
3.2.24.2	Kaplan-Meier Estimates of Time to the First Onset of Treatment-Emergent Adverse Events of Special Interest by MedDRA Preferred Term	Safety	X
3.2.24.3	Kaplan-Meier Estimates of Longest Duration of Treatment-Emergent Adverse Events of Special Interest by MedDRA Preferred Term	Safety	X

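### Onset of each adverse event of special interest is summarised by a Kaplan-Meier median that will very probably not be estimable for events below about 40% incidence; incidence at fixed times should be named instead

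*SAP*

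**What the plan says.** Section 9.2.2 lists the AESIs as separate events, among them colitis, pneumonitis, intestinal perforation, several individual infections and ALT or AST elevations. It sets the method for onset, "The time to onset of the first occurrence of each AESI will be analyzed using the KM method", and then names one statistic: "Median time to onset of the first occurrence of each AESI will be estimated by the KM method". The censoring rule is "Participants with no AESI at the time of analysis will be censored at the time of analysis". The same section limits the analysis of AESI duration to "participants in the safety population with at least 1 occurrence of the AESI". It writes no such limit for onset, so onset is estimated over everyone in the safety population.

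Section 9.2.3 lists the output as "Median time to the first onset of treatment-emergent AESIs by MedDRA PT". Appendix A gives Table 3.2.24.2 a broader title, "Kaplan-Meier Estimates of Time to the First Onset of Treatment-Emergent Adverse Events of Special Interest by MedDRA Preferred Term", and plans Figure 4.3.1 under the same title. Appendix A also plans AESI frequencies (Table 3.2.24.1) and life-table summaries of all treatment-emergent events, including Table 3.2.22, "Summary of Treatment-Emergent Adverse Events by MedDRA Preferred Term: Life-Table Method".

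**The concern.** A KM median over a whole population is the time by which half of that population is estimated to have had the event. For an uncommon event that time is never reached, and the table cell reads not estimable. The AESIs are specific events, each analysed on its own, and reporting by preferred term can split the grouped items further.

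The summary meant to describe when each named risk appears may therefore be empty for most rows, in both arms. The crude percentages in Table 3.2.24.1 are not a full substitute. Section 9.1 excludes data after crossover from the treatment comparison, and Section 5.2 lets control participants cross over before Week 24, so length of observation can differ between arms.

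**Working it through.** **Plan's own figure.** There is none to reproduce: the SAP gives no AESI rate and no expected median. The question is how often the named statistic would exist.

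**Inputs.** The planned size is 212 randomised 1:1, so 212 / 2 = 106 per arm (Sections 1 and 3.1). Enrolment lasts 1 year and the expected study duration is 4 years (Section 3.3). As a smaller-sample case I use 32 per arm, the approximate arm size at the interim analyses (Section 10.1). Incidence is assumed, so a range is shown.

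**Condition.** The KM median exists if S(t) ≤ 0.5 at some time within follow-up. With no earlier censoring, this means that at least half of the arm has the event: P(X ≥ n/2), X ~ Binomial(n, p). For n = 106 the threshold is 53 participants, and for n = 32 it is 16.

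**Simulation, 106 per arm.** 3,000 replicates, exponential onset, uniform entry over 1 year, analysis at 4 years. One version censors event-free participants at the analysis date. A second counts events only up to 35 days after the last dose, with an assumed discontinuation rate of 0.5 per year, and carries event-free participants to the analysis date as Section 9.2.2 writes. In both, the row label is the underlying 4-year risk.

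Chance that the median exists:

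| Assumed incidence | Exact, 106 | Exact, 32 | Simulated, staggered entry | Simulated, written censoring rule with discontinuation |
|---|---|---|---|---|
| 10% | <0.00001 | <0.00001 | 0.0007 | 0.0003 |
| 20% | <0.00001 | 0.0001 | 0.003 | 0 of 3,000 |
| 30% | 0.00001 | 0.014 | 0.009 | 0 of 3,000 |
| 40% | 0.02 | 0.16 | 0.06 | 0.0003 |
| 50% | 0.54 | 0.57 | 0.48 | 0.001 |
| 60% | 0.99 | 0.91 | 0.94 | 0.002 |

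In the last column the chance is still only 0.17 at an underlying 4-year risk of 80%.

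**Does heavy censoring rescue the median?** When few remain at risk, a late event can pull the curve to 0.5 although fewer than half of the arm had the event. With event-free participants censored 35 days after the last dose instead, the simulated chance at 106 per arm is 0.015 at 20%, 0.04 at 30% and 0.13 at 40%. So half of the arm is an approximate threshold, but the conclusion below 40% stands.

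**What a fixed-time estimate would give.** With no earlier censoring, the approximate 95% CI is p ± 1.96 × √(p(1 − p)/106):
- p = 5%: 0.9% to 9.1%
- p = 10%: 1.96 × √(0.10 × 0.90/106) = 5.7 points, so 4.3% to 15.7%
- p = 20%: 12.4% to 27.6%

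An estimate by arm is therefore available throughout the range where the median is not.

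**The case against.** The strongest reply is that the plan already shows AESI risk over time. A reader might infer from the median wording that it does not, and the documents do not support that reading. Figure 4.3.1 is a KM figure of time to first AESI onset, which shows cumulative risk at every time and needs no median. Tables 3.2.22 and 3.2.23 give interval proportions by preferred term, with an effective sample size adjusted for censoring (Section 9.2.1). Section 9.2.2 names the KM method before it names the median. Table 3.2.24.2 is titled as KM estimates and marked as a standard table, and its shell is not shown, so it may hold more than a median.

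This removes the claim that risk by time is absent. It does not supply a stated AESI estimate at a fixed time with an interval: the text commits to none, and the life tables are not described as applying the AESI thresholds (Grade 2 or higher, or at least 5 times the upper limit of normal).

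Two further replies have some force. Not estimable is a correct KM result, not an error. The SAP also expects sparse data: Section 9.1 allows listings in place of tables, and Section 9.2.3 says that a listing may suit 10 or fewer participants. Both are options, and neither replaces the median for an event too common for a listing but well short of half of an arm.

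A reader might also extend the point to time to first symptom-score response (Section 7.4.2.4), because Section 3.3 assumes response rates of 10% to 35%. That does not follow. Those are responder rates at Week 24, with missing data, discontinuation and early crossover counted as non-response (Section 7.4.2.2). Time to first response counts any qualifying 7-day average from Day 7 onward, so its cumulative rate may be higher. KM curves and a stratified log-rank test are planned there as well.

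**Conclusion.** The point holds in a limited form. The only onset statistic that Sections 9.2.2 and 9.2.3 name will very probably not be estimable for any AESI affecting fewer than about 40% of an arm. At 106 per arm and 40% incidence, the chance that it exists is about 0.02 exact and 0.06 with staggered entry; at 20% it is below 0.00001 exact and 0.003 with staggered entry.

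This rests on assumed incidences, exponential onset and an assumed discontinuation rate. It cannot be said that every AESI row will be empty: the list includes Grade 2 or higher diarrhea and rash, no rates are given, and near 50% incidence the median is about as likely to exist as not. The study ended early (Section 5.3); a shorter follow-up makes the median harder to reach, but by how much cannot be worked out from the SAP.

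No primary or key secondary test is touched. Severity is low: a descriptive safety output has a weak headline statistic where a better one is available from the same data.

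**What to change.** In Sections 9.2.2 and 9.2.3 and in Table 3.2.24.2:
- Make the onset summary the cumulative incidence of each AESI at prespecified times, for example Weeks 12 and 24, by arm, with 95% CI and numbers at risk.
- State how death is handled, as a competing event or as censoring, and apply the crossover cut of Section 9.1.
- Report the KM median only where the curve reaches 0.5.
- Give median onset among affected participants only as a description, labelled as conditional on having the event.

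The cost is a few lines of SAP wording and a change to one table shell, which Appendix A marks as standard. No new data are needed, and the planned figure and life tables can stay as they are.
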